**Criteria for Evaluation:**

**Efficacy Measures:** T25FW (measured in seconds but calculated to feet/second), MSWS-12, TUG (seconds), and 2MWT (meters)

**Safety Measures:** Adverse events (AEs), safety laboratory tests (hematology, clinical chemistry, and urinalysis), vital signs (blood pressure and pulse rate), Columbia-Suicide Severity Rating Scale (C-SSRS), and Expanded Disability Status Scale (EDSS)

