**Table 4: Physical Examination Assessments Relating to Safety (Continued)**

Assessment	Study Visit	Description
Expanded Disability Status Scale (EDSS)	Week 52	The Expanded Disability Status Scale (EDSS) is an ordinal scale, 0 to 10, based on a comprehensive neurological examination, used to quantify disability in multiple sclerosis. The EDSS utilizes scoring in 8 functional systems (visual, brainstem, pyramidal, cerebellar, sensory, bowel and bladder, cerebral, and other) and ambulation. A score of 0 indicates a normal neurological exam and a score of 10 is death. EDSS steps 1 to 4.5 are defined by functional system scoring in patients who are fully ambulatory. EDSS steps 5.0 to 9.5 are defined by the extent of walking impairment.

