#### **13.1.1. Adverse Event (AE) Definition**

Any medical condition or clinically significant laboratory abnormality with an onset date before the first date of study drug administration is usually considered to be pre-existing, and should not be documented in the CRF as an AE.

An AE **does** include:

- an exacerbation of a pre-existing illness;
- an increase in frequency or intensity of a pre-existing episodic event or condition;
- a condition detected or diagnosed after study drug administration even though it may have been present prior to the start of the study;
- persistent disease or symptoms present at baseline which worsen following the start of the study.

An AE **does not** include:

- medical or surgical procedures (eg, surgery, endoscopy, tooth extraction, transfusion)  
Note: in this case, the condition that led to the procedure is an AE;
- pre-existing diseases or conditions present or detected prior to start of study drug administration, which do not worsen;
- the disease or disorder being studied or a sign or symptom associated with that disease (ie, signs or symptoms associated with lack of efficacy will generally be considered to reflect underlying disease, rather than AEs, and are considered anticipated);
  - In this study, walking ability is an efficacy parameter and changes in this measure (both positive and negative) will be reported as efficacy outcomes. Worsening of other MS-associated parameters should be reported as AEs
- situations where an untoward medical occurrence has not occurred (eg, hospitalization for elective surgery, elective abortion, social, and/or convenience admissions);
- overdose of either study drug or concomitant medication without any signs or symptoms. (Dosing details will be recorded on the appropriate eCRF(s)).
- pregnancy - Pregnancy in itself is not regarded as an AE unless there is a suspicion that an investigational product may have interfered with the effectiveness of a contraceptive medication (see [Section 13.3.3](#)).

All AEs must be fully and completely documented on the AE page of the CRF and in the subject's medical notes. The following attributes must be assigned: description of AE, dates and times of onset and resolution (or whether ongoing), severity ([Section 13.1.6](#)), relationship to study drug ([Section 13.1.7](#)), whether an SAE or not (Section 13.1.2, and action taken (ie, no action taken; study drug interrupted; study drug discontinued; other).

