## 14.6. Safety and Tolerability Analyses

All safety analyses will be based on the Safety analysis set. Adverse events in Study ADS-AMT-MS303 will be recorded starting immediately following completion of the last study procedure for [Study ADS-AMT-MS301](#) at a Week 16 Visit for that study (which also serves as the first visit for Study ADS-AMT-MS303). All AEs will be listed by subject and period of onset: pre-dose and TEAEs.

The incidence of TEAEs will be summarized by treatment sequences 1, 2, and 3, and overall for all subjects. The incidence of the following will be presented by system organ class (SOC) and preferred term (PT) within SOC in the safety analysis set.

- TEAEs
- Investigator-determined treatment-related TEAEs
- TEAEs leading to drug discontinuation
- TEAEs by severity

- Serious TEAEs (STEAEs)
- Investigator-determined treatment-related STEAEs
- Discontinuation due to STEAEs

Clinical laboratory test parameters will be listed for individual subjects and values outside of the reference ranges will be flagged. The incidence of potentially clinically significant changes in laboratory parameters at each study visit will be tabulated. Vital signs measurements at each timepoint will be listed by subject. The incidence of potentially clinically significant changes at each study visit will be summarized.

Descriptive statistics for the mean and mean changes in the C-SSRS will be generated by study visit. Results will also be graphically depicted.

Descriptive statistics for the mean and mean change from ADS-AMT-MS301 Screening value in the EDSS will be generated.

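### EDSS, a listed safety measure that the protocol calls ordinal, is summarised by mean and mean change, with no EDSS-based count of subjects who worsened

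*Combined protocol and SAP*

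**What the plan says.** The synopsis (Criteria for Evaluation) names the EDSS among the safety measures. Table 4 in section 11.1.1 says the EDSS "is an ordinal scale, 0 to 10, based on a comprehensive neurological examination", with 10 meaning death, so a rise is a worsening. It adds that "EDSS steps 1 to 4.5 are defined by functional system scoring in patients who are fully ambulatory" and that "EDSS steps 5.0 to 9.5 are defined by the extent of walking impairment".

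The analysis is one sentence in section 14.6: "Descriptive statistics for the mean and mean change from ADS-AMT-MS301 Screening value in the EDSS will be generated". The synopsis account of the safety analyses does not mention the EDSS. Nowhere do the documents give an EDSS shift table, a threshold for worsening, a proportion worsened or a subject listing.

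Other safety data in section 14.6 are handled subject by subject. For laboratory data, "The incidence of potentially clinically significant changes in laboratory parameters at each study visit will be tabulated", and individual values are listed with out-of-range results flagged. Vital signs also get a listing and an incidence.

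Table 4, section 12.7 and Appendix A schedule the EDSS at Week 52 only. It is absent from the Early Termination procedures in section 12.8 and from that column of Appendix A. The reference value comes from MS301 Screening.

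**The concern.** A safety measure of disability should first show how many subjects got worse. A mean change answers a different question, because it nets those who worsened against those who improved. On an ordinal scale the mean is also hard to interpret. By Table 4's own account, a half-point low on the scale reflects functional-system findings and a half-point high on the scale reflects walking, so equal numerical changes need not be equal clinical changes.

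The practical risk lies in how the result would be read. A mean change close to zero could be reported as stable disability over the extension while an unknown number of subjects had progressed. The primary objective is safety and tolerability, and the EDSS is the scheduled neurological examination that serves it.

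**Working it through.** The plan states no EDSS figure, distribution or threshold, so there is nothing to reproduce. The check is what the stated summary can and cannot reveal.

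**Inputs.** The documents supply the scale direction and type (Table 4), the planned statistic (section 14.6) and the enrolment ceiling of about 540 (section 7.2). The rates and sizes of change below are assumptions for illustration. Using 540 also assumes that every subject has a Week 52 score, so it is an upper bound.

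**Formula.** Mean change = (share worsened × points up) − (share improved × points down).

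**Equal changes of 1.0 point.** With 20% up and 20% down: 0.20 × 1.0 − 0.20 × 1.0 = 0.0. The same zero arises at any equal share:

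| Assumed share worsened (equal share improved) | Worsened of 540 | Mean change | SD of change | Median | Min / max |
|---|---|---|---|---|---|
| 5% | 27 | 0.0 | 0.317 | 0.0 | −1 / 1 |
| 10% | 54 | 0.0 | 0.448 | 0.0 | −1 / 1 |
| 20% | 108 | 0.0 | 0.633 | 0.0 | −1 / 1 |
| 30% | 162 | 0.0 | 0.775 | 0.0 | −1 / 1 |

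**Unequal changes.**
- 10% up 1.0 and 20% down 0.5: 0.10 × 1.0 − 0.20 × 0.5 = 0.0, with 54 of 540 worsened.
- 10% up 1.0 and 30% down 0.5: 0.10 × 1.0 − 0.30 × 0.5 = −0.05, an apparent improvement with the same 54 worsened.

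**Precision does not help.** In the 20% case the 95% half-width for the mean is 1.96 × 0.633 / √540 = 0.053, so the report would show a tight interval around zero. A count from the same data would show 108 subjects, 20.0%, with half-width 1.96 × √(0.20 × 0.80 / 540) = 0.034, or 3.4 percentage points. With 270 subjects it is 54 worsened and a mean of 0.0 ± 0.076.

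**Would a fuller set of descriptive statistics help?** Section 14.5 spells out its descriptive statistics for efficacy as including the standard error, median and extremes. In the table above the median and extremes are the same in every row. The spread does grow with the share who change, but it does not give a number. For example, 5% up and 5% down by 2.0 points gives a variance of 0.05 × 4 + 0.05 × 4 = 0.40, the same as 20% up and 20% down by 1.0 point (0.20 + 0.20 = 0.40). The first has 27 worsened and the second 108. The extremes would differ, but they show only that someone changed by that much.

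**Does another planned table supply the count?** Section 13.1.1 says "Worsening of other MS-associated parameters should be reported as AEs", and section 9.8 treats an MS exacerbation or worsening as an adverse event, so some of these subjects appear in the TEAE tables. Section 13.1.1 also assigns changes in walking, good or bad, to efficacy, and walking is what sets scores of 5.0 and above. On the efficacy side, section 14.4 counts those who gain at least 20% in T25FW speed. Those who slow down are grouped with the unchanged as non-responders. Walking decline therefore enters the efficacy means, but no planned table counts the subjects who had it.

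**The case against.** Several counter-arguments have force.

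- **A reader might infer that no worsened subject is counted anywhere.** The documents do not support that. Worsening of MS other than in walking is to be reported as an adverse event, and section 14.6 tabulates TEAEs by system organ class, preferred term and severity. What is missing is a count based on the EDSS itself. The adverse event route depends on what is reported, not on the scheduled examination.
- **The plan may intend more than a mean.** If the section 14.5 usage carries over, the median and extremes are already included. Section 14.5 also leaves analysis detail to an SAP, and no SAP text on the EDSS is in the documents. Both points stand, so the gap is shown only for the text available. Neither yields a number worsened.
- **A reader might infer that a walking gain hides worsening of vision, bladder or other functions within one subject.** Table 4 gives little support. At 5.0 and above the total follows walking, so functional-system worsening would hardly register whether or not walking improved. Below 5.0 the subject is fully ambulatory and the functional systems set the score. Offsetting within a subject is mostly limited to crossing that boundary. The arithmetic shows cancellation across subjects.
- **A count has limits too.** The study has one arm, section 5.1 describes MS as usually progressive, and the change also spans the MS301 period. A count of worsened subjects cannot be attributed to the drug. That is correct, and it applies equally to the mean.
- **The stakes are limited.** No objective names the EDSS, it is scheduled once in this study, and no test or decision depends on it.

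**Conclusion.** The point holds as a reporting weakness in a safety measure. As written, section 14.6 gives the EDSS a summary that suits its stated ordinal nature poorly and states no EDSS-based count of subjects who worsened, while laboratory and vital-sign data beside it get an incidence. A mean change of zero, or slightly better, is compatible with anything from no worsened subjects to well over 100 of 540 (108 at an assumed 20%, 162 at an assumed 30%).

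The cancellation is arithmetic and does not rest on those rates. The particular numbers do, because the documents give no EDSS distribution. For the same reason the documents do not show how many subjects score 5.0 or above, although the enrolled population has walking impairment. Adverse event reporting narrows the gap without closing it. The effect is on how safety is described, and no inferential result is affected.

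**What to change.** In section 14.6, and in the SAP, add to the EDSS sentence:

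- a shift table of total EDSS score from MS301 Screening to Week 52;
- the median change;
- the number and percentage worsened, unchanged and improved, by treatment sequence and overall.

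Prespecify the threshold for worsening and state it in points, not steps. Table 4 labels steps at half-point values, so a one-step change could be read as 0.5 or 1.0. The documents supply no threshold; the sponsor should choose and justify one before the data are reviewed.

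State the denominator and show subjects with no Week 52 EDSS as a separate missing row. This matters because section 8.5 withdraws subjects who stop study drug and no EDSS is scheduled at Early Termination. A percentage among those assessed describes only those who reached Week 52.

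Keep the mean and mean change as a supplement. Summarise functional-system scores separately only if they were captured as data at both time points. Table 4 says the EDSS uses them, but the documents do not say that they are recorded individually. A table of total scores alone would not recover functional-system worsening at 5.0 and above.

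The total-score table needs no new assessment. The cost is one additional descriptive table, which should be presented with the caution that it has no comparator.

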#### **14.7. Demographics and Baseline Characteristics**

Demographic and baseline characteristics (age at Week 0, gender, weight, height, BMI, race, ethnicity, medical history, physical examination) will be listed for individual subjects and will be summarized. Demographic data and key baseline characteristics will be summarized for the MITT and safety populations.

#### **14.8. Prior and Concomitant Medications**

All prior and concomitant medications will be assigned a generic name and a drug class based on the World Health Organization (WHO) Dictionary. Prior and concomitant medications will be listed and summarized.

#### **14.9. Completion of the Study and Withdrawals**

Withdrawals and the reason for withdrawal will be tabulated. The number and percentage of subjects who complete the study will be summarized. The number and percentage of subjects who withdraw from the study will be tabulated by treatment sequence. Study drug discontinuations will be summarized in a similar fashion.

#### **14.10. Protocol Deviations**

Significant protocol deviations will be listed and categorized (for example, deviations related to entry criteria, dosing, prohibited concomitant medications, other).

## **15. DIRECT ACCESS TO SOURCE DATA/DOCUMENTS**

### **15.1. Study Monitoring**

Sponsor representatives and regulatory authority inspectors are responsible for contacting and visiting the investigator for the purpose of inspecting the facilities and, upon request, inspecting the various records of the study (eg, CRFs and other pertinent data), provided that subject confidentiality is respected.

The study monitor is responsible for inspecting the CRFs at regular intervals throughout the study to verify the following: adherence to the protocol; completeness, accuracy, and consistency of the data; and adherence to local regulations on the conduct of clinical research. The monitor should have access to subject medical records and other study-related records needed to verify the entries on the CRFs. The investigator must agree to cooperate with the monitor to ensure that any problems detected in the course of these monitoring visits are resolved.

### **15.2. Audits and Inspections**

Authorized representatives of the sponsor, a regulatory authority, an Independent Ethics Committee, or an Institutional Review Board may visit the site to perform audits or inspections, including source data verification. The purpose of the sponsor audit or inspection is to systematically and independently examine all study-related activities and documents to determine whether these activities were conducted, and data were recorded, analyzed, and accurately reported according to the protocol, Good Clinical Practice (GCP) guidelines of the International Council on Harmonization (ICH), and any applicable regulatory requirements.

In accordance with ICH GCP and the sponsor audit plans, this study may be selected for an audit. Inspection of all site facilities (eg, pharmacy, drug storage areas, laboratories) and study-related records contained within these facilities are subject to inspection during an audit.

The investigator should contact the sponsor immediately if contacted by a regulatory agency about an inspection.

### **15.3. Subject Confidentiality**

The investigator must ensure that each subject's anonymity is maintained. Subjects will be identified by a unique Subject Identification Number. Study related documents should be kept in strict confidence by the investigator in compliance with applicable regulations and ICH GCP Guidelines. The investigator and Institution must permit authorized representatives of regulatory agencies, and the IRB/research ethics board (REB)/independent ethics committee (IEC) direct access to review the subject's original medical records for verification of study-related procedures and data. Direct access includes examining, analyzing, verifying, and reproducing any records and reports that are needed for the evaluation of the study. The investigator is obligated to inform the subject in the ICF that the above-named representatives may review study-related records from subjects.

### **15.4. Case Report Forms**

Electronic CRFs will be completed for each enrolled subject. The participants of the study will not be identified by name on any study documents to be collected by the sponsor or designee.

The PI is required to review and sign-off on all eCRFs. The sign-off is done by an electronic signature within the electronic data capture system (EDC). Also, a CD of all site specific subject data (including PI approval, audit history, and discrepancies) will be sent to each site that has subject data in the system for archival purposes.

## **16. QUALITY CONTROL AND QUALITY ASSURANCE**

To ensure compliance with Good Clinical Practices and all applicable regulatory requirements, the sponsor may conduct a quality assurance audit. Please see [Section 15.2](#) for more details regarding the audit process.

## 17. ETHICS

### 17.1. Ethics Review

The PI must obtain IRB/REB/IEC approval for the investigation. Initial IRB/REB/IEC approval, and all materials approved by the IRB/REB/IEC for this study including the ICF and recruitment materials must be maintained by the investigator and made available for inspection.

This study will be conducted in accordance with the US Code of Federal Regulations (CFR) governing the protection of human subjects (21 CFR 50), IRB/REB/IEC (21 CFR 56), the obligations of clinical investigators (21 CFR 312), and ICH GCP guidelines.

The sponsor expects the PI to comply with local IRB/REB/IEC requirements. The investigator will also comply with current standards of GCP, particularly in reference to the safety and rights of the subjects. Investigators are encouraged to discuss any ethical issues that arise prior to or during the conduct of the study with the sponsor.

The PI at the site is responsible for obtaining IRB/REB/IEC approval for the final protocol, sponsor-approved ICF, and any advertisements to recruit subjects. Written approval of these documents must be obtained from the IRB/REB/IEC before any subject is enrolled at a site.

The PI is also responsible for the following interactions with the IRB/REB/IEC:

- Obtaining IRB approval for any protocol amendments and ICF revisions before implementing the changes;
- Providing the IRB/REB/IEC with any required information before or during the study;
- Submitting progress reports to the IRB/REB/IEC, as required, during the conduct of the study; requesting re-review and approval of the study, as needed; providing copies of all IRB/REB/IEC re-approvals and relevant communication to the sponsor;
- Notifying the IRB/REB/IEC of all serious and unexpected adverse events related to the study drug reported by the sponsor, as required.

### 17.2. Ethical Conduct of the Study

This study will be conducted in compliance with GCP according to the ICH guidelines (Topic E6: Guideline for Good Clinical Practice), US Code of Federal Regulations (21 CFR), and local ethical and legal requirements that are consistent with the most current version of the Declaration of Helsinki.

### 17.3. Written Informed Consent

The sponsor must review the draft ICF prior to submission to the IRB/REB/IEC for approval. An IRB/REB/IEC -approved copy of the ICF will be forwarded to the sponsor or designee.

Written informed consent will be obtained from all study subjects prior to any tests or evaluations. The contents and process of obtaining informed consent will be in accordance with all applicable regulatory requirements.

The ICF documents the study-specific information the investigator provides to the subject and the subject's agreement to participate. Among other things, the investigator or designee will fully explain in layman's terms the nature of the study, along with the aims, methods, potential risks, and any discomfort that participation may entail, as well as insurance and other procedures for compensation in case of injury. It will be explained that the study is for research purposes only and may not provide any therapeutic benefit to the individual. The investigator must also explain to the volunteers that they are completely free to refuse to enter the study or to withdraw from it at any time without prejudice. Each subject will acknowledge receipt of this information by giving written informed consent for participation in the study.

Each subject must sign and date the ICF before any study-related procedures are performed. When a protocol amendment (see Section 17.4) substantially alters the study design or the potential risks or burden to subjects, the ICF will be amended and approved by the IRB/REB/IEC, and all active subjects will again provide informed consent. The original and any amended signed and dated ICF(s) must be retained in the subject's file at the study site and a copy must be given to the subject.

The ICF must comply with all applicable US Code of Federal Regulations (21 CFR 50), and ICH Good Clinical Practice guidelines. It should also include any additional information required by local laws relating to institutional review. A statement that subject medical records must be available for investigations into SAEs must be included in the ICF. It should also include any additional information required by local laws relating to institutional review.

